6.2.4.10 Recording of diet

Participants will begin their randomized diets following the oral glucose tolerance test and flexible sigmoidoscopy at dinner. Participants will be instructed to consume only the food provided and no other food. Participants must eat all of the brownie and servings of sorbet provided. Participants will have access to additional food outside of the meals provided, however, the entire serving of the previous meal must have been consumed. The amount of food consumed will be recorded on the case report forms.

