6.2.4.11 Timing of meals

The first meal will be served following the oral glucose tolerance test or after the flexible sigmoidoscopy. All scheduled snacks and meals will be provided following the oral glucose tolerance test except during the flexible sigmoidoscopy. Lunch will be served at approximately 12:30h and dinner at approximately 18:00h. A snack will be provided at 15:00h and 21:00h. Beginning at the dinner meal, all participants will consume one serving of brownie or sorbet (15 gm) per day that contain 0 or 2.5 gm CMC per serving. Participants will be expected to finish each meal by the time of their next meal. There will be no limitation on the time to consume snacks. All food must be consumed by midnight.

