6.2.5.6 Timing of meals

Breakfast will be served at 09:00h. Lunch will be served at approximately 12:30h and dinner at approximately 18:00h. A snack will be provided at 10:30h, 15:00h and 21:00h on Days 2-9. Participants will be expected to consume snacks by the next meal with the last snack consumed by midnight on Days 2-9. On Day 10, the 21:00h intervention snack will be provided in addition to the intervention and meal at 18:00h. Participants will be expected to finish each meal by the time of their next meal or snack. Lunch should be finished within 30 minutes. On Day 10, all food must be consumed by 19:30h. No food or beverage other than water is to be consumed between midnight and breakfast on Days 2-9 and between 19:30h and breakfast on Day 10.

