6.2.5.7 Satiety Questionnaire

On days 2, 3, 5, 6, 9 and 10, participants will complete a standard food satiety questionnaire at 12:15h before lunch and at 13:00h following the completion of lunch.

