7.2.2 Comparison of metabolites between diets with and without CMC

The first analysis will compare the abundance of fecal and plasma metabolites between the two dietary groups. As assignment to the diet will be based on randomization, the primary analysis will be an unadjusted t-test to compare the concentration of the various metabolites measured in the plasma and feces. As there will be multiple comparisons, we will report both nominal (p values) and q values accounting for the multiple testing.

7.2.3 Effects of CMC consumption on a range of inflammatory and metabolic parameters that characterize metabolic syndrome

Weight change will be compared between the treatment groups from day 1 to day 11 using a t-test. If there is evidence of confounding despite randomization, additional analyses will use linear regression adjusted for change in weight from day 1 to day 11 and BMI at day 0.

We will also assess changes to each subject regarding satiety (from the questionnaire re food adequacy/sufficiency). These data are on visual analogue scale so will be compared using unpaired t-test for between group comparisons or paired t-tests for within group comparisons.

The area under the glucose and insulin concentration curves during the oral glucose tolerance test at day 1, day 11 and the change from day 1 to day 11 will be compared between groups using a t-test. The $\Delta I_{30}/\Delta G_{30}$ will be used as a measure of

beta cell function⁴⁵ while homeostasis model assessment of insulin resistance (HOMA-IR) will be used to estimate insulin resistance⁴⁶ and compared between the groups with a t-test at the same time points.

Sera will be assayed for a range of hormones and cytokines using a customized bead-based assay designed to include immune inflammatory and metabolic markers of obesity and type 2 diabetes (includes IL-8, IL-6, TNF α , lipocalin-2, MCP1, insulin, leptin, ghrelin, ESR, CRP) all of which are known to be elevated in metabolic syndrome (performed at GSU). Additionally, fecal samples will be assayed for lipocalin-2 by ELISA. These data will be compared using unpaired t-test for between group comparisons or paired t-tests for within group comparisons.

8 Safety and Adverse Events

Adverse Event

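### Every satiety score is taken after CMC has started, so the planned within-participant changes cannot measure change from before CMC

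*Combined protocol and SAP*

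**What the plan says.** Section 7.2.3 (effects on inflammatory and metabolic parameters) says of the questionnaire: "We will also assess changes to each subject regarding satiety". The visual analogue scores are to be compared by unpaired t-test between groups or paired t-test within groups. No reference day or time is given for the change.

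Section 6.2.5.7 fixes the schedule: "On days 2, 3, 5, 6, 9 and 10, participants will complete a standard food satiety questionnaire at 12:15h before lunch", repeated at 13:00h after lunch. Section 6.1.6 and the table in section 6.2 agree. No satiety scale is scheduled at screening, Visit 2, the washout days or Day 1.

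Section 6.2.4.10 gives the start of exposure: "Participants will begin their randomized diets following the oral glucose tolerance test and flexible sigmoidoscopy at dinner". Section 5 adds that brownie and sorbet servings come with all three meals and the scheduled snacks, at 0 or 2.5 g CMC per serving. The Study Summary gives 15 g per day in six divided doses. Sections 5 and 6.2.4.11, however, also speak of one serving per day: "Beginning at the dinner meal, all participants will consume one serving of brownie or sorbet" is followed there by a per-day wording.

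**The concern.** A change score, or a paired test within the CMC arm, says something about CMC only if one of the two values was taken off CMC. Here none is. If part of the effect on fullness or hunger is already present by Day 2, using Day 2 as the reference subtracts it. What remains within a single arm is also mixed with everything else that alters appetite over an inpatient stay.

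Other Aim 3 measures do not have this gap. Weight, the glucose tolerance test and the PROMIS scale are all taken on Day 1 before the first CMC serving. Satiety also bears on the reading of the weight result: section 6.2.2.3 treats weight as an outcome and leaves food quantity unadjusted, and section 5 allows extra food on request.

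**Working it through.** **1. Servings before the first satiety score.** Inputs are the meal times in sections 6.2.4.11 and 6.2.5.6, and servings at every meal and scheduled snack (section 5).

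- Day 1, from dinner on: "Lunch will be served at approximately 12:30h and dinner at approximately 18:00h. A snack will be provided at 15:00h and 21:00h". Dinner at 18:00h and the 21:00h snack give 2 servings.
- Day 2: "Breakfast will be served at 09:00h", and "A snack will be provided at 10:30h, 15:00h and 21:00h on Days 2-9". Breakfast and the 10:30h snack give 2 servings.
- Total before 12:15h on Day 2: 4 servings × 2.5 g = 10 g, which is 10/15, or two thirds, of the stated daily amount. The Day 2 lunch serving makes it 5 × 2.5 = 12.5 g by the 13:00h repeat.

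If one serving per day is meant literally, the count is lower, but the Day 1 dinner serving still comes first. Under either wording, the number of pre-CMC satiety scores is 0.

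**2. The plan's own power figures.** Section 7.1 claims 80% power for Aim 3 at 1.51 SD between groups and 1.15 SD for paired analyses. Noncentral-t power with 8 per arm and two-sided alpha 0.05 (assumed; the plan states neither level nor sidedness) gives 0.802 and 0.796. Both figures reproduce.

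**3. What a Day 2 reference loses.** Let f be the fraction of the CMC effect present by lunch on Day 2. Change from Day 2 then retains 1 − f of the effect. For illustration, take a total effect of 1.15 SD of the paired difference, so the paired test has effect size 1.15 × (1 − f) with n = 8:

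| f | effect size | power |
|---|---|---|
| 0 | 1.15 | 0.80 |
| 0.25 | 0.86 | 0.56 |
| 0.5 | 0.58 | 0.29 |
| 0.75 | 0.29 | 0.11 |
| 1 | 0 | 0.05 |

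The documents give no value for f; the table shows the whole range. The same factor 1 − f applies to a between-arm test of change from Day 2: the subtraction happens in the CMC arm only, so randomization does not restore what was removed.

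**4. Precision lost without a baseline covariate.** Adjusting for a baseline with correlation r to the outcome leaves residual variance (1 − r²). With r = 0.5 to 0.7 (assumed), r² = 0.25 to 0.49 of the variance is removed. The detectable between-arm difference would fall from 1.51 SD to 1.51 × √0.75 = 1.31 SD, or 1.51 × √0.51 = 1.08 SD. This ignores the one degree of freedom spent on the covariate.

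**The case against.** **Change from Day 2 is only one reading.** Each assessment is a pair of scores around one lunch, so the changes in section 7.2.3 may mean 12:15h to 13:00h. That is a fair reading and the plan does not exclude it. Under it the pre-lunch score serves as a same-person reference, and the between-arm contrast of meal response is randomized. But both scores are on CMC, so a paired test within the CMC arm still has no off-CMC value.

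**A reader might infer that satiety cannot show a CMC effect at all.** The documents do not support that. The plan lists an unpaired between-group test, and randomization makes the comparison of on-treatment scores valid without a baseline. An effect that builds after Day 2 would also show in between-arm differences in change.

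**The early exposure is small in the longer view.** By 12:15h on Day 10 the six-dose schedule gives 51 or 52 servings (the 10:30h snack is stated only for Days 2-9), that is 127.5 or 130 g. So 10 g is about 8% of that cumulative exposure. This stands: the documents do not claim a fast effect on fullness, and f may be small.

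**Day 1 lunch is an awkward baseline.** It follows a fast, a 75 g glucose load and possibly the sigmoidoscopy; it comes without the brownie or sorbet; and it covers only one of the two alternating menus. This also stands. It rules out Day 1 lunch as a within-arm reference, but not as a covariate, because the conditions are the same in both arms. More generally, a baseline would not free a within-arm paired test from confounding with time in hospital.

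**Conclusion.** The concern holds for the change and within-group analyses. With no score before Day 1 dinner, they cannot measure change from before CMC. They miss whatever effect exists by Day 2, and within one arm they cannot separate CMC from the hospital stay. This does not depend on how the serving wording is resolved; only the figure of four servings (10 g) does.

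The between-arm comparison of on-treatment scores remains valid. Its loss is precision: 25% to 49% of residual variance under the assumed correlation of 0.5 to 0.7, for which the documents offer no figure. Aim 3 is worded as exploratory and section 3.2 specifies no efficacy or safety endpoints, so the importance is modest.

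**What to change.** Give the same scale once before the first CMC serving, at 12:15h and 13:00h around Day 1 lunch or, alternatively, at Visit 2 or on a washout day. Use it only as a covariate in a between-arm comparison of mean satiety over the six questionnaire days. Those days form three consecutive pairs (2-3, 5-6, 9-10), so each pair covers both menus. State whether the outcome is the pre-lunch score, the post-lunch score or the difference. Do not interpret within-arm paired tests as CMC effects.

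If no pre-CMC scale is added, delete the change and within-group tests for satiety and compare the arms on the six-day mean. That is a text edit only.

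Separately, reconcile the one-serving-per-day wording in sections 5 and 6.2.4.11 with the six divided doses in the Study Summary.

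The cost of the first option is two short questionnaires per participant. On Day 1 participants are already in the unit, but the score would follow the glucose test and possibly the sigmoidoscopy, equally in both arms. A Visit 2 score would reflect the usual diet, and a washout score would be completed at home.

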1.3.1 Risk-Benefit Balance

The risks associated with participating in this controlled feeding experiment are low. The diets will be constructed to meet all nutritional requirements. The CMC will be purchased from Modernist Pantry and is the same as that which is sold to small bakeries throughout the United States. Thus, consumption of the study diet entails no greater risk than consumption of a typical American diet outside of the study procedures.

Participants will undergo phlebotomy and sigmoidoscopy with biopsy. There is a small potential risk for complications of sigmoidoscopy, including bleeding and perforation. The risks of these complications are estimated to be less than 1% for bleeding and less than 0.1% for perforation. Patients with contraindications to biopsy will be excluded. The risks of phlebotomy include bleeding, infection, phlebitis, and fainting. As with all research, there is a small risk of loss of confidentiality. Participants may also experience some discomfort associated with eating a limited diet for 14 days. Participants may also feel tired and/or discomfort from staying in the hospital for the 11 day inpatient stay.

In summary, the risk of serious or severe adverse events is likely extremely low. While there is no direct benefit expected for the participants, the balance of the participants' risk vs. the knowledge to be gained is believed to be favorable.

2 Study Objectives

The specific aims for our proposal are:

1. Establish a tractable and physiologic means of administering and measuring CMC consumption and its metabolic impact in healthy volunteers.
2. Examine extent to which CMC consumption impacts human gut microbiota composition, gene expression, and/or localization.
3. Explore effects of CMC consumption on a range of inflammatory and metabolic parameters that characterize metabolic syndrome.

3 Study Design

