4.4 Early Withdrawal of Participants

4.4.1 When and How to Withdraw Participants

Participants may be withdrawn from the study at any time if the investigator or the participant believes that the participant's safety will be jeopardized by continued participation, or if the participant does not follow study procedures. Likewise, participants will be withdrawn from the study if they withdraw consent.

5 Study Intervention

All foods will be prepared within the CHPS's metabolic kitchen without emulsifiers (unless specifically added). All participants will follow the same Western style diet (i.e. the only difference being portion size). The macronutrient percentages of calories for the study diet will be 55% carbohydrate, 30% fat, and 15% protein. The diet will be composed of two menus that will be consumed on alternating days. Water, coffee and tea will be provided as desired. Participants will have access to additional food outside of the meals provided, however, the entire serving of the previous meal must have been consumed. The additional food provided outside of the scheduled meals will consist of the food from the same Western style diet provided for each meal.

For the three days prior to admission, participants will be eating an emulsifier free diet at home. Food will be provided by the CHPS metabolic kitchen. After admission to CHPS, no emulsifiers will be consumed prior to dinner on Day 1. Thus, accounting for the 8 hours of nil per os status prior to admission, all participants will have approximately 80 hours of emulsifier free washout time prior to administration of the food containing CMC.

Participants will be randomly assigned to receive 0 or 15 gm per day of CMC (8 participants in each arm of the study). Beginning with the dinner meal on Day 1, all participants will consume one serving of brownie or sorbet (15 gm) per day that contain 0 or 2.5 gm CMC per serving. The brownie and sorbet servings will be provided at all three scheduled meals and scheduled snacks. Prior to eating any other food on the study menu, participants must consume the brownie and sorbet servings.

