7.1 Sample Size Determination

We will recruit the minimum number of subjects to provide adequate statistical power for the aims of the project. For aim 1, statistical power will depend on the prevalence of detectable CMC in the feces of participants at the end of follow-up. We anticipate that in the CMC treated group, the prevalence will be 100% and in the untreated group the prevalence will be 0%. However, with 8 subjects per group, we will have 89% power to detect a difference if the true prevalence of detectable CMC after 2 weeks of a high dose CMC and CMC free diet are 90% and 10%, respectively. For aim 2, power calculation were based on preliminary data in which the difference in mean distance of the nearest bacteria to the epithelium between patients with and without diabetes was 19.13 μ m. The within group standard deviation (SD) for patients without diabetes was 7.17. The within group SD for those with diabetes was even smaller. With a sample size of 8 subjects per group and assuming a within group SD of 7.17, we will have 90% and 80% power to detect a difference in the distance of the nearest bacteria to the epithelium between the treatment groups (CMC vs. no CMC) that is 35% and 44% smaller than the difference observed between patients with and without diabetes, respectively. In Aim 3, the study will have 80% power to detect a difference between

groups equal to 1.51 units of SD. For paired analyses within treatment groups, there will be 80% power to detect a difference of 1.15 units of SD.

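### Section 7.2.3 offers within-arm paired t-tests as an unranked alternative to the between-arm test, but a within-arm change does not isolate the effect of CMC

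*Combined protocol and SAP*

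**What the plan says.** Aim 3 (Section 2) is to "Explore effects of CMC consumption on a range of inflammatory and metabolic parameters that characterize metabolic syndrome". Section 7.2.3 takes its title from that aim. For the serum hormones and cytokines and fecal lipocalin-2 it states: "These data will be compared using unpaired t-test for between group comparisons or paired t-tests for within group comparisons". For satiety it states: "These data are on visual analogue scale so will be compared using unpaired t-test for between group comparisons or paired t-tests for within group comparisons". It does not rank the two tests, limit the "paired t-tests for within group comparisons" to description, or name the days to be paired. In the same section, weight change, the glucose and insulin areas under the curve, the beta-cell index and HOMA-IR are compared between groups only.

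Section 7.1 plans 8 participants per group. For Aim 3 it gives 80% power for a difference between "groups equal to 1.51 units of SD", and then adds: "For paired analyses within treatment groups, there will be 80% power to detect a difference of 1.15 units of SD".

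Section 5 describes what both arms share: "All participants will follow the same Western style diet". Supplied emulsifier-free food is eaten at home for three days before admission. Both arms then stay as inpatients to Day 11, and from dinner on Day 1 both eat brownie and sorbet servings, with or without CMC. Section 6.2.3.2 places the Visit 2 blood and stool samples before the supplied diet begins. Section 6.2.5.7 schedules the satiety questionnaire on Days 2, 3, 5, 6, 9 and 10.

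**The concern.** A paired test within the CMC arm asks whether that arm changed. Aim 3 asks whether CMC changed it. The two questions coincide only if nothing else moves the outcome between the paired days, and here several things could: admission to an inpatient unit, the daily brownie and sorbet, and continued adjustment to a diet begun three days earlier. If Visit 2 is used as the baseline, which the text does not rule out, the whole switch from habitual diet is added.

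The control arm is there to remove these shared changes, and a within-arm p value does not use it. Finding significance in the CMC arm but not in the control arm does not repair this, because that pattern is not a test of the difference between arms. With the choice left open and a separate power figure attached, a within-arm result could be presented under the Aim 3 heading as evidence about CMC.

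**Working it through.** **Inputs.** From Section 7.1: 8 per group, 80% power at 1.51 SD between groups, 80% power at 1.15 SD for paired analyses. Alpha and sidedness are not stated; 0.05 two-sided is assumed.

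**Reproducing the plan's figures (noncentral t).**

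- Paired: df = 8 − 1 = 7; noncentrality = 1.15 × √8 = 3.25. Power is 79.6%, and the difference detectable with 80% power is 1.156 SD.
- Two-sample: df = 16 − 2 = 14; noncentrality = 1.51 × √(8/2) = 3.02. Power is 80.2%, and the difference detectable with 80% power is 1.507 SD.

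Both stated figures reproduce. One-sided 0.05 would give 89.8% and 89.0%, which supports the two-sided assumption. The arithmetic in 7.1 is sound; the issue is what the paired test estimates.

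**What the paired test picks up when CMC does nothing.** Let both arms shift by s, in SDs of within-person change, with no CMC effect. The documents do not give s, so a range is shown. The paired test is then significant with probability p, its power at s with n = 8. The arms are independent, so the CMC arm alone is significant with probability p(1 − p).

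| Shared shift s | CMC arm significant, p | CMC arm alone significant, p(1 − p) | Between-arm test of change |
|---|---|---|---|
| 0 | 5.0% | 4.8% | 5% |
| 0.25 | 9.4% | 0.094 × 0.906 = 8.5% | 5% |
| 0.5 | 23.2% | 0.232 × 0.768 = 17.8% | 5% |
| 0.77 | 46.8% | 0.468 × 0.532 = 24.9% | 5% |
| 1.0 | 68.1% | 0.681 × 0.319 = 21.7% | 5% |

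The third column cannot exceed 25%, the maximum of p(1 − p). A simulation of 200,000 trials at s = 0.5 gave 23.3%, 17.8% and 5.0% for the last three columns.

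**Power if only the between-arm test is used.** At 1.15 SD of change, noncentrality = 1.15 × √(8/2) = 2.30 with df = 14, and power is 57.2%. At 1.51 SD it stays at 80.2%.

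**Timing.** Day 1 fasting blood is drawn before the first CMC serving, and a stool sample is brought from the day before or the morning of admission, so a pre-CMC value is available for serum markers and fecal lipocalin-2. Satiety is first recorded at lunch on Day 2, after CMC has started at dinner on Day 1, so it has no pre-CMC value to pair with.

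**The case against.** The plan has a good deal in its favour.

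- A reader might infer that the valid analysis is missing. It is not: the between-group test is listed for each of these outcomes, and Section 7.2.2 makes an unadjusted between-group t-test primary for metabolites because diet is randomised.
- A reader might infer that the sponsor intends to prove a CMC effect from a within-arm p value. No sentence says so. The wording can be read as matching each kind of comparison to its test, and for satiety a paired test could simply compare before and after lunch. Aim 3 is exploratory, and Section 3.2 sets no efficacy endpoints.
- A reader might count controlled activity among the shared changes. Section 5.4 holds daily steps within 10% of each participant's own pre-admission average, so activity is not a main confounder.
- A Day 1 baseline already follows three days on the supplied diet, so a Day 1 to Day 11 pair leaves out the initial switch.
- A reader might take 1.15 against 1.51 SD to show that the paired test needs a smaller effect. The two share a scale only if the between-arm outcome is a change score, which Section 7.1 does not state.
- The larger error rates need large assumed shifts; at 0.25 SD the excess is small.

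These points limit the concern without removing it. Neither test is ranked, no baseline is named, the paired analysis carries its own power claim, and a Day 1 baseline still leaves the inpatient stay, the vehicle and continuing adaptation in the change.

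**Conclusion.** The point holds as a gap in the hierarchy of tests for serum markers, fecal lipocalin-2 and satiety. The weight, glucose tolerance and HOMA-IR comparisons are unaffected. With no CMC effect, a shared shift of 0.25 to 1.0 SD of change makes the CMC-arm paired test significant in 9% to 68% of trials, and the CMC arm alone significant in 8.5% to 25%, against 5% for the between-arm test of change.

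These figures assume 8 per arm, two-sided 0.05, normally distributed changes, and the same shift and SD in both arms. The true shift is unknown, so the table shows exposure to error and is not a forecast. The documents do not support the stronger reading that the planned Aim 3 analysis is invalid or that a within-arm claim will be made; they leave that route open.

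**What to change.** - State in Section 7.2.3 that the between-arm comparison is the only test of a CMC effect.
- For serum markers and fecal lipocalin-2, compare Day 11 values between arms, adjusted for the pre-CMC (Day 1) value, and name that baseline.
- For satiety, compare the arms at named measured days, for example Days 9 and 10, with no Day 1 adjustment because no such value exists.
- Label within-arm changes as descriptive, and label the 1.15 SD sentence in Section 7.1 the same way.

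The cost is wording: no added participants or visits. The downside is that the 1.15 SD figure no longer supports Aim 3. On the change-score scale, between-arm power at 1.15 SD is about 57%, and the 80% claim rests on 1.51 SD.

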3.2 Primary Study Endpoints

This is not an efficacy study. There are no pre-specified efficacy or safety endpoints for this study. Rather, we will use an unbiased approach to determine the composition of the microbiota and metabolome.

4 Participant Selection and Withdrawal

[figure not shown]

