6.1.7 Oral glucose tolerance test

On day 1 and 11, participants will complete a 2.5 hour oral glucose tolerance test. This test will be completed prior to breakfast following a 12 hour fast. At 08:00h, a catheter will be placed in an antecubital or forearm vein for blood sampling, with the arm placed in a heating pad to promote arterialization of venous blood. After 20 min of acclimatization to the catheter placement, baseline blood samples will be taken at -5 and -1 min prior to the ingestion of 75 grams anhydrous oral glucose over a 5 min period starting at $t = 0$ at ~08:30h. Subsequent blood samples will be collected at $t = 15, 30, 60, 90,$ and 120 min post-ingestion. All samples will be collected on ice into chilled EDTA tubes with protease inhibitor cocktail containing DPP4-inhibitor added immediately, centrifuged at 4 degrees C, aliquoted in ice, and stored at minus 80 degrees C until biochemical analysis. A total of 4 ml of blood will be collected at each

test. Glucose, free fatty acids, insulin, glucagon, and GLP-1/GIP will be the substances tested.

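### Section 7.2.3 compares the glucose and insulin indices between arms at Day 1, Day 11 and on change without naming the deciding test or adjusting for Day 1; one baseline-adjusted analysis per index would serve better.

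*Combined protocol and SAP*

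**What the plan says.** Section 7.2.3 takes the areas under the glucose and insulin curves from the oral glucose tolerance test (OGTT) and states that values "at day 1, day 11 and the change from day 1 to day 11 will be compared between groups using a t-test". The 30-minute insulin/glucose index and HOMA-IR are then "compared between the groups with a t-test at the same time points". The section does not say which of these comparisons answers the question about CMC.

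The timing is clear. Section 6.1.7 states: "On day 1 and 11, participants will complete a 2.5 hour oral glucose tolerance test", before breakfast. Section 6.2.4.10 states: "Participants will begin their randomized diets following the oral glucose tolerance test and flexible sigmoidoscopy at dinner". Section 5 adds that "no emulsifiers will be consumed prior to dinner on Day 1". The Day 1 OGTT is therefore a pre-exposure measurement.

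No ranking of tests is supplied elsewhere. Section 3.2 states: "There are no pre-specified efficacy or safety endpoints for this study". The only covariate adjustment in Section 7.2.3 is a regression on weight change and BMI, to be used if confounding is suspected. It does not include the outcome's own Day 1 value. The q values promised for metabolites in Section 7.2.2 are not repeated in Section 7.2.3.

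Section 5 plans "8 participants in each arm of the study". For Aim 3, Section 7.1 claims 80% power for a difference between "groups equal to 1.51 units of SD", without saying whether this refers to the Day 11 value or to the change.

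**The concern.** The three comparisons differ in what they can show, yet the plan gives them equal standing.

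- **Day 1.** Any difference is due to chance, because randomization precedes the test and CMC follows it.
- **Day 11.** This can show an effect, but leaves between-person variation that Day 1 could explain in the error term.
- **Change.** This uses Day 1, but with a fixed coefficient of 1. That adds noise when the two days are only moderately correlated.

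The last two address the same effect and can fall on opposite sides of 0.05, with no rule for what is then concluded. An analyst could report whichever is more striking. With 8 participants per arm, the precision lost by ignoring or over-subtracting baseline also matters. The documents name the OGTT response as one of the metabolic markers of interest (Section 3.1), so the point touches a planned result and not a side analysis.

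**Working it through.** **Number of tests.** Change is named explicitly for the two AUCs. For the other two indices the plan refers to time points, which may or may not include change.
- Without change for those two: 3 + 3 + 2 + 2 = 10.
- With change: 4 × 3 = 12.

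**The plan's own figure.** Two-sample t-test, 8 per arm, two-sided 0.05 (assumed; Section 7.1 states no alpha): power at 1.51 SD is 80.2%. The stated 80% reproduces.

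**Why the methods differ.** Let the SD be σ on both days, ρ the Day 1 to Day 11 correlation and n = 8 per arm. The variance of the estimated arm difference, in units of 2σ²/n, is:
- Day 11 alone: 1
- Change: 2(1 − ρ)
- ANCOVA on Day 1: (1 − ρ²) × (1 + 1/(2n − 4)) = (1 − ρ²) × 13/12, where the second factor is the price of estimating the slope from 16 people

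| ρ | Day 11 | Change | ANCOVA |
|---|---|---|---|
| 0.3 | 1.00 | 1.40 | 0.91 × 13/12 = 0.99 |
| 0.5 | 1.00 | 1.00 | 0.75 × 13/12 = 0.81 |
| 0.7 | 1.00 | 0.60 | 0.51 × 13/12 = 0.55 |
| 0.8 | 1.00 | 0.40 | 0.36 × 13/12 = 0.39 |
| 0.9 | 1.00 | 0.20 | 0.19 × 13/12 = 0.21 |

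Change improves on Day 11 only when ρ exceeds 0.5. ANCOVA is at least as precise as both from 0.3 to 0.8, and falls marginally behind change at 0.9. The documents give no ρ, so the whole range is an assumption.

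**Simulation.** 100,000 trials per setting, bivariate normal data, 8 per arm, two-sided 0.05.

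Power at a true effect of 1.51 SD:

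| ρ | Day 11 | Change | ANCOVA |
|---|---|---|---|
| 0.3 | 80.1% | 66.1% | 80.4% |
| 0.5 | 80.1% | 80.2% | 87.4% |
| 0.7 | 80.1% | 95.1% | 96.1% |
| 0.8 | 80.1% | 99.3% | 99.2% |

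False positives per index with no effect:
- Day 11 or change significant: 8.8% (ρ = 0.3) to 9.6% (ρ = 0.8).
- One ANCOVA: 4.9% to 5.1%.

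Exactly one of Day 11 and change significant:
- True effect 1.51 SD: 27.5%, 23.4%, 20.2% and 19.9% for ρ = 0.3, 0.5, 0.7 and 0.8.
- No effect: 7.7% to 9.1%.

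**Skewed data.** Suppose the outcome is lognormal with log-SD 0.8, ρ = 0.5 and an effect of 1.51 log-scale SD (all assumed). Raw-scale ANCOVA then has 68% power and the raw change test 71%. After a log transform these data are normal, and the ρ = 0.5 row of the power table applies: 87% and 80%.

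**The case against.** **The aim is exploratory.** Section 2 says Aim 3 will explore effects, and Section 3.2 disclaims endpoints. All the comparisons are prespecified, and each keeps its own 5% level if all are reported. This stands. A reader might infer that a trial-level error rate is broken, but the documents claim none. The 9–10% describes what happens if either result may be taken as the finding.

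**The Day 1 test is a harmless balance check.** Section 7.2 already plans baseline comparisons. This largely stands. A reader might count all three tests and quote a false-positive rate of about 12% per index, but a p value from before CMC would hardly be read as a CMC effect. The remaining criticism is that the Day 1 test is uninformative and listed alongside the others.

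**The test count is uncertain.** A reader might say flatly that every index is tested three times, 12 in all. The wording for the 30-minute index and HOMA-IR does not settle that.

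**The tests do not contradict each other in substance.** A reader might take a difference in significance as opposite findings. At 1.51 SD the two estimates differ in sign in under 1% of simulated trials, and with no effect the verdicts differ in only 8–9% of trials. What varies is which side of 0.05 each falls on.

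**ANCOVA is partly a preference.** Naming change as the principal test would also remove the ambiguity. At ρ = 0.7 ANCOVA gains only 1 point over change, and on raw skewed data it can lose. Both are true. The case for ANCOVA is that ρ is unknown: change loses 14 points at 0.3 and 7 at 0.5, whereas ANCOVA loses almost nothing anywhere. The skewness argument calls for a log scale and does not favour the change test.

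**Conclusion.** The point holds as a recommended improvement to an exploratory analysis. The plan sets 10 to 12 between-arm tests on four indices, names no deciding test, includes a comparison that cannot bear on CMC, and never adjusts for the Day 1 value it collects.

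The harm is twofold. The first is room for selective reading: about 9–10% against 5% per index when nothing is happening, and differing verdicts in 20–28% of trials at the effect size in Section 7.1. The second is lost power: up to 14 points against change at ρ = 0.3, and up to 16 points against Day 11 at ρ = 0.7.

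These sizes rest on normal data, equal SDs on both days, two-sided 0.05 and an assumed correlation of 0.3 to 0.8, none of which the documents supply. That the Day 1 test is pre-exposure and that no deciding test is named follow from the text alone.

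**What to change.** Replace the two OGTT sentences in Section 7.2.3 with:

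> For each index (glucose AUC, insulin AUC, 30-minute insulin/glucose index, HOMA-IR) the between-arm effect is estimated once, by ANCOVA of the Day 11 value on arm with the participant's own Day 1 value as covariate, using log-transformed Day 1 and Day 11 values for positive, right-skewed indices such as HOMA-IR. Day 1, Day 11 and change values are summarised by arm without p values. Any regression on weight change and BMI is supplementary.

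The analysis scale of each index should be fixed before unblinding. The 30-minute index is a ratio of increments and can be zero or negative, in which case a log is not available and its scale needs its own statement.

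The change uses data already collected and reduces 10 to 12 tests to 4. It costs one residual degree of freedom (13 instead of 14) and a marginal loss against the change test at very high correlation: at ρ = 0.9 and 0.75 SD, 86.3% against 87.7%. It does not control multiplicity across indices. Four tests at 5% leave 1 − 0.95⁴ = 18.5% chance of at least one false positive if they were independent, so the results should still be labelled exploratory.
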